For maintenance of anaesthesia, isoflurane will be administered at a concentration of 1.2-2%, and the patient will be mechanically ventilated using parameters that will achieve normal end-tidal CO₂ (35-45 mmHg) and oxygen saturation (> 95%). To maintain relaxation atracurium will be given as 0.1 mg/kg every 20 minutes.

Intraoperative hemodynamics will be measured at 10 min intervals, both heart rate and blood pressure values (SBP, DBP and MAP) will be recorded. Bradycardia defined as heart rate below 60 beats per minute, and bradycardia will be managed if heart rate drops below 55 bpm by giving atropine 0.04 mg/kg IV bolus to be repeated after 5 minutes if needed. Hypotension also described as SBP below 90 mmHg will be managed by giving ephedrine 5-10 mg IV bolus.

At the end of surgery, patients will be given 1 g acetaminophen IV, and NSAID will be given in the recovery room in the form of ketorolac 30 mg IV.

For recovery, neuromuscular blockade will be reversed using neostigmine 0.04 mg/kg and atropine 0.02 mg/kg, and the patient will be extubated fully awake and when adequately reversed which is clinically assessed as the patient achieves tidal volumes > 5ml/kg.

Patients will be transferred to the post anesthesia care unit (PACU), and same intraoperative hemodynamics will be measured every 10 min through their PACU stay duration. With regards to postoperative management, Visual analog scale (VAS), which is a scale from 0 to 10 where 0 represents no pain at all and 10 represents the most severe pain, will be used to assess pain. VAS assessment will be carried out during the 1st hour at the PACU then at 2, 4, 6, 12, and 24 hours postoperative during day 1, and If VAS is >4, opioids will be administered in the form nalbuphine 5mg IV, and the time to first dose and total number of doses given will be noted not to exceed 60 mg per day. Also, hand grip power will be assessed at the PACU then at 2, 4, 6, 12, and 24 hours postoperatively, and this will be done using the digital dynamometer. The readings will be compared with a measurement of the patient's baseline grip power of the same hand taken before surgery and with readings taken after block administration.

3. Measurement tools

- Hand grip power will be measured using digital dynamometer at these intervals: immediately postoperative at PACU and then at 2, 4, 6, 12, and 24 hours postoperative, and results compared with baseline measurement.
- Time for full recovery of hand grip power.

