- Intraoperative hemodynamics in the form of heart rate and mean blood pressure every 10 minutes.
- Postoperative pain will be measured using VAS score at these intervals: immediately postoperative at PACU and then at 2, 4, 6, 12, and 24 hours postoperative.
- Postoperative hemodynamics in the form of heart rate and mean blood pressure in PACU every 10 minutes until discharge
- Time to first opioid dose
- Total amount of opioid administered.
- Patient satisfaction will be measured at 24 hours postoperative using self reported satisfaction scale (1= very dissatisfied and 5=very satisfied)

VI. Study outcomes

1. Primary outcome

- Time for full recovery of hand power, defined as time from start of block activation till time of achieving grip strength similar to patient's baseline

2. Secondary outcome(s)

- Hand grip power after surgery at PACU, then at 2, 4, 6, 12, and 24 hours.
- Time to first analgesia request
- VAS score after surgery at rest and during movement at PACU then at 2, 4, 6, 12, and 24 hours

- Patient satisfaction score at 24 hours postoperative
- Intraoperative hemodynamics

Statistical Analysis

I. Sample size

Based on a previous study (12) the duration of motor block in patients receiving ISB was 711 ± 151 min (REF). A minimum sample of 50 patients is needed to detect a 20% reduction in duration of motor block. The study power was set at 90% and alpha error was set at 0.05. Sample size was calculated using the MedCalc Software V14. The number of envelopes will be increased to 60 (30 in each group) to compensate for dropouts.

II. Statistical analysis

Statistical package for social science (SPSS) software, version 26 for Microsoft Windows (SPSS inc., Chicago, IL, USA) will be used for data analysis. Categorical data will be presented as frequency (%) and will be analyzed by the chi square test. Continuous data will be checked for normality using the Shapiro-Wilk test and will be presented as mean (standard deviation) or median (interquartile range) as appropriate. Continuous data will be analyzed using unpaired the t test or the Mann Whitney test according to normality of the data. Repeated measures will be analyzed using the analysis of variance (ANOVA) for repeated measures with post-hoc pairwise comparisons using the Bonferroni tests. A P-value less than 0.05 will be considered statistically significant.

References

- (1) Farmer KW and Wright TW. Shoulder arthroscopy: the basics. *J Hand Surg Am.* 2015 Apr; 40(4):817-21.

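### Grip is not read between 6 h and 12 h after surgery, where both design means for recovery time fall, so the stated 90% power is not delivered

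*Combined protocol and SAP*

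**What the plan says.** The primary outcome (VI. Study outcomes) is a continuous time, "defined as time from start of block activation till time of achieving grip strength similar to patient's baseline". Under V.3 Measurement tools, postoperative grip is measured "immediately postoperative at PACU and then at 2, 4, 6, 12, and 24 hours postoperative, and results compared with baseline measurement". The only other readings are the preoperative baseline and one before induction. Time to full grip recovery has its own line in that list, but no testing method, diary or interpolation rule goes with it.

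The sample size section states that "the duration of motor block in patients receiving ISB was 711 ± 151 min", that "A minimum sample of 50 patients is needed to detect a 20% reduction in duration of motor block", and that "The study power was set at 90% and alpha error was set at 0.05". It adds: "The number of envelopes will be increased to 60 (30 in each group) to compensate for dropouts".

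For the analysis, "Continuous data will be analyzed using unpaired the t test or the Mann Whitney test according to normality of the data". No time-to-event or interval-censored method is named.

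**The concern.** The sample size treats each recovery time as known to the minute. The schedule shows only that recovery happened between two readings. If the true times in both arms mostly fall between the same two readings, most patients receive the same recorded visit whichever block they had. Much of the contrast the trial was sized to detect is then lost.

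Two things are at stake. The trial may miss the difference it was designed to find. Even a significant result would come with an effect estimate that depends on the visit times as much as on recovery.

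**Working it through.** **Inputs.** Interscalene mean 711 min, SD 151, 20% reduction, power 90%, alpha 0.05, 50 patients, 60 envelopes (Sample size). Wait after block 30 min (V.2 Study Protocol). Surgery 90-120 min (IV. Eligibility Criteria). Readings at PACU, 2, 4, 6, 12 and 24 h (V.3). Assumptions: normal times, equal SDs, 0-30 min for induction and emergence, and recovery recorded at the first reading at or after it occurs.

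**1. The plan's own figure.** The difference is 0.20 × 711 = 142.2 min, so the PENG mean is 568.8 min. Two-sided, n per arm = 2 × (1.960 + 1.282)² × 151² / 142.2² ≈ 23.7, or 24. The t-based version gives 24.7, so 25 per arm and 50 in total. With exact times, t-test power is 90% at 25 per arm and 95% at 30. The stated N reproduces.

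**2. Moving to the postoperative clock.** Block to end of surgery is 120-150 min from the plan's figures, or up to 180 min with the assumed allowance.

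| Offset | Interscalene mean | PENG mean |
|---|---|---|
| 120 min | 591 min = 9.9 h | 448.8 min = 7.5 h |
| 150 min | 561 min = 9.4 h | 418.8 min = 7.0 h |
| 180 min | 531 min = 8.9 h | 388.8 min = 6.5 h |

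Both means stay in the 6-12 h gap until the offset exceeds 568.8 − 360 = 208.8 min. The gap is 360 / 142.2 ≈ 2.5 times the target difference.

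**3. Where patients are recorded.** At a 150-min offset, the 6 h and 12 h readings fall 510 and 870 min after the block.
- Interscalene: z = (510 − 711)/151 = −1.33 and (870 − 711)/151 = 1.05. So 9% are recorded by 6 h, 76% at 12 h and 15% at 24 h.
- PENG: z = −0.39 and 1.99. So 35% are recorded by 6 h, 63% at 12 h and 2% at 24 h.

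Over offsets of 120-180 min, 74-77% of interscalene and 56-69% of PENG recoveries fall in the gap.

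**4. Effect on the t-test.** At 150 min the recorded SDs rise to about 291 and 238 min, while the mean difference rises only to about 197 min. The pooled SD is √((291² + 238²)/2) ≈ 266. The standardised difference falls from 142.2/151 = 0.94 to 197/266 = 0.74. Approximate power at 25 per arm is Φ(0.74 × √12.5 − 1.96) ≈ 0.74-0.75. Simulation gives 75%.

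**5. Simulated power at the plan's 20% effect, offsets 120-180 min.**

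| Schedule and analysis | 25 per arm | 30 per arm |
|---|---|---|
| Exact times, t-test | 90% | 95% |
| Present schedule, plan's rule (Mann-Whitney), timed from block | 54-59% | 62-68% |
| Present schedule, Mann-Whitney on the visit label | 73-77% | 82-86% |
| Present schedule, t-test regardless of normality | 73-77% | 81-84% |
| Present schedule, interval-censored normal likelihood-ratio test | 79-81% | 85-88% |
| 8 h and 10 h added, Mann-Whitney | 85-87% | not run |
| 8 h and 10 h added, interval-censored | 89-91% | not run |

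On the present schedule Shapiro-Wilk rejects in essentially every trial, so the plan's rule selects Mann-Whitney. Row 2 is lowest because, timed from the block, patients first seen recovered at 12 h differ only in theatre time, and the test ranks that noise as if it were recovery. Varying the offset with an assumed SD of 15 min around 120, 150 and 180 min gives 55%, 58% and 62% at 25 per arm. The last row should be read as about 90%, since grouped times cannot carry more information than exact ones.

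**6. Effect on the estimate.** For a true difference of 142 min, the recorded median difference averages about 14-52 min and the recorded mean difference about 193-204 min.

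**The case against.** **The lowest figure depends on an unstated rule.** Comparing the visit at which recovery was first seen, rather than minutes from block, raises Mann-Whitney power to 73-77% at 25 per arm. This stands as a reason to quote a range. But the plan's outcome clock starts at the block, so the lower figure follows the definition as written, and the higher one still misses 90%.

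**The 568.8 min figure is a design margin, not a prediction for PENG.** The hypothesis is motor sparing, and a larger effect would be easier to see. With a PENG mean of 500 min (about 30% shorter), even the block-clock Mann-Whitney reaches 90% at 25 per arm. At 427 min (40% shorter) it exceeds 99%. This is correct, but the plan claims 90% power at 20%, and that claim fails.

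**Recovery may be timed separately.** It has its own line in the measurement list, and near-continuous timing would deliver the stated power. No such procedure is described, so the sponsor should be asked. As written, only the scheduled readings exist.

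**The bias depends on the summary.** The median difference is understated and the mean difference overstated. That is true, and either way the estimate is distorted by the schedule.

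**Conclusion.** The concern holds. At the plan's own assumptions, the written schedule and tests give about 54-59% power at 25 per arm on the outcome as defined, and at most about 77% on the kindest reading. Filling all 60 envelopes with no losses gives 62-68%, or at most about 86%, although the extra ten are meant for dropouts. The recorded median difference would typically be about a third of the true value or less.

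This rests on normal times with equal SDs, recovery recorded at first detection, and a block-to-end-of-surgery time of 120-180 min, part of which is assumed. Midpoint assignment gives nearly the same t-test power. Type I error is not inflated (4-5% under the null), so the problem is lost power and a distorted estimate, not false positives. It should be corrected before data collection, because readings not taken between 6 h and 12 h cannot be recovered later.

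**What to change.** 1. **Analyse the primary outcome as interval-censored.** Recovery lies between the last reading below the baseline criterion and the first reading that meets it. Use interval-censored regression or a generalised log-rank test in place of the t-test or Mann-Whitney on visit times. The criterion needs a numerical definition for the intervals to be fixed. If recovery is to be timed in some other way, the method should be written down.
2. **Restate the power.** On the present schedule with this analysis it is about 79-81% at 25 per arm and 85-88% at 30 per arm.
3. **Preferably add grip readings at 8 h and 10 h**, with the same dynamometer and blinded assessor. With the interval-censored analysis this restores about 90% at 25 per arm.

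Items 1 and 2 need only changes of wording, and the stated power becomes less favourable. Item 3 costs two short readings per patient, taken by the assessor who already collects the 6 h and 12 h data. Keeping the schedule and adding patients would take about 36-40 per arm by t-test (offsets 90-180 min) and would not repair the estimate.

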The aim of the study is to compare the effect of PENG block and interscalene block on the motor power of the hand and time to full recovery of motor affection if any.

Objectives:

- To assess effectiveness of PENG block in recovery of hand motor power compared with ISB
- To compare between PENG and ISB in controlling postoperative pain
- To assess effectiveness of PENG block in reducing postoperative opioid consumption compared with ISB

Hypothesis

We hypothesize that PENG block will be superior to interscalene nerve block regarding motor power sparing.

Ethical Considerations

This study will be conducted after taking approval of the research ethical committee. Written informed consent will be obtained from study participants or their legally authorized representative.

Methodology

I. Study design

Randomised comparative single blinded superiority study.

II. Study setting and location

This study will be conducted at the theatre for orthopedic surgeries at The Cairo University Teaching Hospital.

III. Study population

Patients scheduled for arthroscopic shoulder surgery

IV. Eligibility Criteria

1. Inclusion criteria

- Adult patients (age 22-60) scheduled for arthroscopic shoulder surgery under general anesthesia
- Both genders
- ASA grade I-II
- BMI less than 35
- Duration of surgery 90-120 minutes

2. Exclusion criteria

- ASA grade III-IV
- Allergy to local anesthetics
- Coagulation disorder (INR >1.2, Platelets <100,000), or recent intake of clopidogrel or warfarin within 1 week.
- Active infection at site of injection

V. Study Procedures

1. Randomisation

This is a single centre randomised comparative trial. Patients undergoing arthroscopic shoulder surgery will be randomised to receive either PENG block, which is the intervention group, or to receive interscalene block.

Randomisation will be done via computer generated random numbers which will be enclosed in envelopes with 60 envelopes in total, 30 for each group. This is a single blinded study so an anesthesiologist who will not partake in this study will open the envelopes and proceed with the allocated block. After the procedure, the anesthesiologist who will assess motor power recovery and collect postoperative data will also be blinded to the type of block given. Therefore, to reduce bias only the anesthesiologist and main researchers will be aware of the allocation, while the outcome data collector will be blinded.

2. Study Protocol

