needle is in the correct position. Afterwards 15 ml of 0.25% bupivacaine will be injected to complete the block. A wait time of 30 minutes will be allowed before induction of general anesthesia to ensure the full activation of the block.

Group I (Interscalene block):

Patients in this group will also receive ISB prior to general anesthesia. With patient placed in supine position and head facing away from the side being blocked, the skin is disinfected first then the linear ultrasound probe is placed transversely on the neck to identify the carotid artery. Then the transducer is moved slightly laterally until middle and anterior scalene muscles are identified with the brachial plexus between them then local infiltration will be done using 29 G needle to apply 3 mL lidocaine 2%. A 22-gauge needle will be introduced in plane in a lateral-medial direction aiming towards the space between the roots. After a 3 ml saline injection for confirmation of proper position, 15 ml of 0.25% bupivacaine will be injected with advancement of the needle as the roots are displaced by the injectate. Adequate injection will be confirmed by visualizing the roots being surrounded by the local anesthesia infiltrate.

Patients receiving either block will wait 30 minutes before induction of general anesthesia. Interscalene block will be tested using pin prick test on shoulder and upper arm area, by loss of shoulder abduction, and finally by passively moving the arm to check for loss of previously present pain on movement. PENG block will be tested using pin prick test and loss of pain on passive movement as well. A block not fulfilling these examinations will be

deemed unsuccessful, and the patients will be given additional opioids in the form of morphine 5 mg IV with induction of general anesthesia. These patients will be excluded from the study. Before induction of general anesthesia another dynamometer measurement will be recorded.

In both groups patients will receive general anaesthesia using the standard centre preferences; IV induction via propofol 2 mg/kg and fentanyl 1 mic/kg for induction, then atracurium 0.5 mg/kg for intubation followed by 0.1 mg/kg every 20 minutes for maintenance. An additional dose of fentanyl 1 mic/kg will be administered on skin incision.

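### Time to first rescue opioid has no value for a patient not rescued by 24 h, and the tests named for it come with no censoring or ranking rule

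*Combined protocol and SAP*

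**What the plan says.** All references are to the combined protocol and SAP.

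- **Event.** V.2 Study Protocol makes rescue conditional: "If VAS is >4, opioids will be administered in the form nalbuphine 5mg IV, and the time to first dose" is to be noted.
- **Follow-up.** The same section sets the schedule: "VAS assessment will be carried out during the 1st hour at the PACU then at 2, 4, 6, 12, and 24 hours postoperative". No pain check is scheduled after 24 h.
- **Outcome name.** VI.2 Secondary outcome(s) lists "Time to first analgesia request"; V.3 Measurement tools lists "Time to first opioid dose".
- **Time origin.** None is stated for this outcome. The primary outcome in VI.1 has one: "defined as time from start of block activation".
- **Analysis.** Statistical Analysis II says: "Continuous data will be analyzed using unpaired the t test or the Mann Whitney test according to normality of the data". The other methods named there are chi-square for categorical data and repeated-measures ANOVA. Censoring, survival methods, and a rank or substitute value for a patient who needs no rescue are not mentioned anywhere.

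**The concern.** A patient whose VAS stays at 4 or below through the last check has a time to first rescue known only to exceed the follow-up. That is a right-censored value, and neither a t-test nor Mann-Whitney has anything to use for it unless a rule supplies it. The analyst could leave the blanks out, enter 24 h, or rank these patients last. The answers differ, and the choice would be made after the data are seen.

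Leaving blanks out is what happens if the named tests are simply run on the recorded times. The comparison is then between patients who needed rescue in each arm, so it is no longer the randomised comparison. The patients for whom analgesia worked best contribute nothing. At stake is one secondary outcome that serves the pain and opioid objectives.

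**Working it through.** **The plan's own figure.** The documents give no figure for this outcome. The sample size concerns motor block and is not in dispute: a 20% reduction from 711 min is 142.2 min, and with SD 151, 90% power and two-sided 0.05 (sidedness assumed), the two-sample t-test needs 24.7, so 25 per arm, or 50 in total, as stated.

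**Inputs.** From the documents: 30 per arm, two-sided 0.05, and a 24 h limit. Assumed: log-normal rescue times with median m and coefficient of variation CV.

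**Never-rescued share.** σ = √ln(1 + CV²), z = ln(24/m)/σ, share = 1 − Φ(z).

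- CV 0.4: σ = 0.385. m = 20 h: z = 0.473, share 32%. m = 15 h: z = 1.22, share 11%.
- CV 0.5: σ = 0.472. m = 14 h: share 13%. m = 10 h: share 3%.
- CV 0.4: m = 12 h: share 4%. m = 9 h: share 0.5%.

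**Power by simulation** (at least 1,500 runs per case; repeat runs agree within about two percentage points):

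| Never rescued, arm 1 vs arm 2 | Mann-Whitney, blanks dropped | Mann-Whitney, never-rescued ranked last | Log-rank |
|---|---|---|---|
| 32% vs 11% | 44% | 77% | 73% |
| 13% vs 3% | 60% | 75% | 70% |
| 4% vs 0.5% | 74% | 77% | 74% |
| none vs none | 97% | 97% | 96% |

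The last row uses medians of 11.85 and 9.48 h with CV 0.21, borrowed from the plan's motor-block figure and only indicative.

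**Direction.** Among the rescued, the mean time is m·exp(σ²/2)·Φ(z − σ)/Φ(z). With everyone kept and capped at 24 h, it is that mean × Φ(z) + 24 × (1 − Φ(z)). CV is 0.4 throughout.

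- *Toward zero* (medians 20 vs 15 h): rescued only, 16.9 − 14.5 = 2.4 h; all patients, 19.2 − 15.6 = 3.6 h.
- *Away from zero* (30% in each arm never needing rescue; medians 10 vs 7 h in the rest): rescued only, 10.57 − 7.53 = about 3.0 h; all patients, 0.7 × (10.73 − 7.54) = about 2.2 h.
- *Sign reversed* (40% vs 10% never needing rescue; medians 7 vs 10 h in the rest): rescued only, about −3.0 h; all patients, (0.4 × 24 + 0.6 × 7.54) − (0.1 × 24 + 0.9 × 10.73) = 14.12 − 12.06 = about +2.1 h.

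In the last two patterns, the few log-normal times beyond 24 h count as never rescued. Both patterns are constructed to show what can happen.

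**Ties at 24 h.** If rescue occurred only at scheduled checks (PACU coded as 1 h), giving never-rescued patients the value 24 h would tie them with patients rescued at 24 h. Power would be 47% against 70% when they are ranked above 24 h (32% vs 11%), and 65% against 69% (13% vs 3%).

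**The case against.** The strongest objection is that every material loss rests on an assumed never-rescued share. The plan describes a single-injection block with one stated dose each of acetaminophen and ketorolac, and nothing in it points to a large unrescued group. The case built on the plan's own motor-block figure shows no loss, and at 4% vs 0.5% dropping blanks does as well as log-rank. This stands. It limits the size of the point but does not fill the gap: every analysed patient has a block that passed testing, plus scheduled non-opioid analgesia, so some going unrescued is plausible.

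Several stronger readings are tempting, and the documents do not support them:

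- *That the plan drops never-rescued patients.* It does not say so; it is silent.
- *That log-rank is required.* In the log-normal cases, ranked Mann-Whitney does slightly better. Under a constant hazard (20% vs 5% never rescued), log-rank leads, 63% to 53%. Either is acceptable once the rule is stated.
- *That the clock starts at the block.* Given "Patients receiving either block will wait 30 minutes before induction of general anesthesia" and "Duration of surgery 90-120 minutes", the limit would then be 24 + 1.5 to 2.0 + 0 to 0.5 = 25.5 to 26.5 h, before induction and emergence time. But the documents attach that origin only to the primary outcome. The rescue sentence sits among postoperative procedures, so a postoperative origin is the natural reading.
- *That rescue can take only six values.* The ceiling of 60 mg per day at 5 mg per dose allows 12 doses against six checks, and one list speaks of a request. Both suggest dosing between checks, though neither proves it.

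It is also fair that this is one outcome among several serving the same objectives. VAS scores and total opioid amount remain.

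**Conclusion.** The point holds as a gap in the method for one unranked secondary outcome, and it should be corrected. Time to first rescue opioid is right-censored at 24 h after surgery, and the named tests, applied to recorded times, would compare a subgroup selected by the outcome.

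The size depends on the unknown never-rescued share. It is a loss of roughly 30 percentage points of power at 32% vs 11%, 10 to 15 points at 13% vs 3%, and essentially nothing if nearly all patients are rescued. A reader might infer that dropping blanks always dilutes the difference. It does so when the arm with later rescue also has more never-rescued patients, but other patterns can inflate or reverse it.

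A reader might also infer that the sample size or the primary result is undermined. This point does not show that. The same sentence on tests also covers time to grip recovery, but that outcome needs its own consideration.

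**What to change.** In Statistical Analysis II, state that every patient in the analysis population (after the failed-block exclusion in V.2) is kept for time to first rescue opioid, and choose one of two methods:

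1. Kaplan-Meier and log-rank, censoring patients without rescue at 24 h after surgery or at last contact, after counting any rescue given at the 24 h check.
2. Mann-Whitney, with never-rescued patients tied above every observed time, including rescue at 24 h. This needs complete 24 h follow-up. The first option also handles a patient last seen earlier, and the sample-size section allows for dropouts.

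Report the number never rescued in each arm. As minor clarifications, state the time origin and express the censoring time from it, and reconcile "Time to first analgesia request" with "Time to first opioid dose" under one name.

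The cost is two or three sentences and slightly more analysis. No new data are needed, and the sample size and primary outcome do not change.

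### No primary test is fixed: if recovery is timed at the scheduled visits, the normality rule leads to a rank test on raw minutes that loses about 11 to 21 points of power at the planned effect

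*Combined protocol and SAP*

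**What the plan says.** - **Test choice** (Statistical Analysis, II): "Continuous data will be analyzed using unpaired the t test or the Mann Whitney test according to normality of the data". Normality is checked by Shapiro-Wilk. The section gives no level for that check, does not say whether it is applied per arm or pooled, and names no separate test for the primary outcome.
- **Sample size** (Statistical Analysis, I): the control figure is a mean of 711 min with SD 151, taken from an earlier ISB study. The section then states "A minimum sample of 50 patients is needed to detect a 20% reduction in duration of motor block". On error rates it says "The study power was set at 90% and alpha error was set at 0.05", and on dropouts "The number of envelopes will be increased to 60 (30 in each group) to compensate for dropouts".
- **Primary outcome** (VI.1): the recovery time is "defined as time from start of block activation till time of achieving grip strength similar to" the patient's own baseline value. The clock therefore starts at the block.
- **Grip readings** (V.2): "hand grip power will be assessed at the PACU then at 2, 4, 6, 12, and 24 hours postoperatively". Apart from a baseline and a pre-induction reading, no other dynamometer readings are described. The protocol does not say how a recovery time is assigned between visits.
- **Timing** (IV and V.2): a 30-minute wait after the block, then surgery of 90 to 120 minutes.

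**The concern.** The sample size rests on a difference in means, but the analysis section does not commit to a test of means. The data choose between a mean test and a rank test, so the hypothesis tested is not fixed in advance, and no effect estimate with a confidence interval is planned.

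This matters in practice because of how the outcome is likely to be recorded. If recovery is noted at the scheduled visits, each value is a fixed visit hour plus that patient's own block-to-end-of-surgery interval. The values then fall in tight clusters, the normality check rejects, and Mann-Whitney is applied to the raw minutes. Patients who recovered at the same visit are not treated as equal: they are ranked by how long theatre took, which says nothing about the block. A real 20% reduction would be missed more often than the stated 90% power suggests.

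**Working it through.** **1. The plan's own figure.** Difference = 0.20 × 711 = 142.2 min, so d = 142.2/151 = 0.942. The normal approximation gives n = 2(1.960 + 1.282)²/0.942² = 23.7 per arm. The noncentral t solution is 24.7, hence 25 per arm, 50 in total, with 90.4% power. A one-sided test would need 20 per arm and does not match. The stated N is a two-sided t-test with equal SDs.

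**2. What visit-recorded data look like.** Assumptions not in the documents:
- normal underlying times with SD 151 in both arms;
- block-to-end-of-surgery interval centred on 150 min;
- PACU reading 0.5 h after surgery;
- anyone not recovered by 24 h set to the 24 h visit.

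The visits then fall at about 180, 270, 390, 510, 870 and 1590 min after the block.

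| First visit with recovery | ISB, mean 711 | PENG, mean 568.8 |
|---|---|---|
| 6 h or before | Φ((510−711)/151) = 9% | Φ((510−568.8)/151) = 35% |
| 12 h | 76% | 63% |
| 24 h | 1 − Φ((870−711)/151) = 15% | 1 − Φ((870−568.8)/151) = 2% |

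Most patients in both arms sit in one cluster, and about half of all ISB–PENG pairs share a visit.

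**3. Why breaking those ties costs power.** The probability that an ISB patient recovers later, counting same-visit pairs as one half, is 0.668. Random offsets leave this unchanged on average but remove the tie correction to the variance.
- Pooled visit shares are 0.003, 0.010, 0.055, 0.153, 0.695 and 0.085, so the tie factor is 1 − Σp³ = 0.659.
- Ties broken, 25 per arm: SE = √(51/7500) = 0.0825, z = 0.168/0.0825 = 2.04, power ≈ Φ(2.04 − 1.96) = 53%.
- Ties kept: z = 2.04/√0.659 = 2.51, power ≈ Φ(2.51 − 1.96) = 71%.

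The gap is about 18 points.

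**4. Simulation** (3,000–4,000 trials per setting, 20% reduction, offset varying ±15 min, Shapiro-Wilk at 0.05). Shapiro-Wilk rejected in 100% of trials in every row, per arm or on pooled residuals.

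| Per arm | Offset midpoint, min | Plan's rule | Fixed t-test | Rank test on visit, ties kept |
|---|---|---|---|---|
| 25 | 120 | 54.1% | 73.2% | 74.2% |
| 25 | 150 | 56.1% | 74.2% | 75.3% |
| 25 | 180 | 61.3% | 76.5% | 76.7% |
| 25 | 210 | 67.7% | 79.7% | 78.6% |
| 30 | 120 | 63.2% | 81.5% | 83.2% |
| 30 | 150 | 65.2% | 82.9% | 83.8% |
| 30 | 180 | 70.5% | 85.8% | 85.9% |
| 30 | 210 | 74.9% | 86.1% | 86.0% |

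The loss against the t-test runs from 11 points (30 per arm, midpoint 210) to 19 (25 per arm, midpoint 120). It reaches 21 with offsets varying by only ±1 min (54.8% against 75.9% for Welch). If the SD shrinks with the mean, the gap to the t-test is about 25 points (53.6% against 78.9% at 25 per arm). Type I error under the plan's rule was 4.6–5.6%.

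**5. Where the loss shrinks or disappears.**
- Exact, normal times: 91.1% (plan) against 91.2% (t-test) at 25 per arm, and 94.6% against 95.0% at 30. Shapiro-Wilk rejects in only 5–10% of trials.
- Identical offset for every patient, so true ties: 76.0% against 75.2% at 25 per arm.
- 30% reduction, varying offsets: 93.5% against 98.3% at 25 per arm, and 96.9% against 99.4% at 30. At 50%, no loss.
- A Mann-Whitney test on raw minutes fixed in advance has the same power as the plan's rule in every visit-recorded setting.

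**6. Side effect on the mean.** With next-visit recording as in step 2, the expected recorded means are 940.0 (ISB) and 743.6 (PENG). The difference is 196.4 min against a true 142.2, an overstatement of 196.4/142.2 − 1 = 38%. Across settings the recorded difference was about 191–200 min.

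**The case against.** The strongest reply is that the figure depends on a recording rule the protocol never states. The list of measurement tools gives time for full recovery as an item separate from the scheduled readings. If times were observed exactly and were normal, as the sample size assumes, the rule would seldom switch tests and would cost almost nothing. This stands, and the figure must carry that condition. The identical-offset case carries less weight, because the protocol itself allows surgery to vary by 30 minutes.

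A reader might go further and infer that letting normality choose the test is itself what loses the power, so that any test fixed in advance would cure it. The documents do not support that. Mann-Whitney fixed in advance on raw minutes loses just as much. The cause is the undefined derivation of time from sparse visits, combined with a rank test that breaks same-visit ties.

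Nor can one infer that the rule always selects the weaker test, or that a Welch t-test should simply become primary. With exact times and 5% late recoverers (an assumption), Welch had 48% power against 79% for the plan's rule. If instead a quarter of PENG patients were fully spared, the ordering reverses. Neither mixture has a source in the protocol. Welch on next-visit times also overstates the reduction.

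Finally, since the hypothesis is motor sparing, the true effect may be well above 20%, and then little is lost. That is fair, but 20% is the effect the trial is sized for.

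**Conclusion.** The point holds in conditional form. The primary test is not fixed, and the derivation of recovery time is undefined. If recovery is recorded at the scheduled visits, the only postoperative grip readings described, the plan ends in Mann-Whitney on raw minutes in essentially every trial. At a 20% reduction that gives about 55–64% power at 25 per arm in most settings tried. A t-test or a tie-keeping rank test on the same data gives 73–78%. The assumptions are normal underlying times, equal SDs of 151, offset midpoints of 120–210 min, and Shapiro-Wilk at 0.05.

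This is a loss of power, not of validity. It comes on top of the cost of the visit schedule, which by itself takes the t-test from about 90% to about 75% at 25 per arm, and from about 95% to about 83% at 30.

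**What to change.** In Statistical Analysis, II:

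1. Remove the normality rule for the primary outcome. Keep Shapiro-Wilk only for choosing how data are displayed.
2. State that recovery time is the first scheduled visit at which grip is back to baseline under the protocol's own definition, and how patients not recovered by 24 hours are classed.
3. Name one primary analysis that keeps same-visit patients tied: Mann-Whitney on the visit of first recovery, or an interval-censored time-to-event analysis. Report an effect estimate with a 95% CI. The visit-based rank test matched or beat the plan's rule in every visit-recorded setting tried, including one with late recoverers (63% against 47%).
4. If wanted, give a Welch mean difference as a sensitivity analysis, noting that on next-visit times it overstates the reduction.

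In Statistical Analysis, I, restate the power for the named analysis: about 75% at 25 per arm and about 83% at 30 under the assumptions above.

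The cost is a few sentences, with no new data, visits or patients. The drawback is that the primary result is expressed in visits or intervals, not as a mean in minutes.
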